10.2. Secondary objectives

Additional endpoints are achievement of response (CR + CRu + PR), as defined in Section 8, overall survival, and safety. Toxicity will be recorded for all patients, separately by grade, type of toxicity, and chemotherapy cycle. For patients treated with Zevalin, subsequent toxicity, including HAMA, will be tabulated separately.

Concerning safety, the R-FND therapy program is known to be safe (24). The use of Zevalin is safe (33,35). The sequential use of Zevalin shortly after chemotherapy is innovative, but not unprecedented ([name], personal communication). The potential for marrow toxicity will be monitored carefully following Zevalin (see Section 7.7).

Treatment related mortality is expected to be rare. Any such events will be reported (see Section 11.4); if 2 or more treatment related deaths occur, the study will be temporarily placed on hold, and discussion about early closure will take place.

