# **Protocol Body**

# **1.0 Objectives**

1.1 To assess whether the time to progression for these high-risk patients can be prolonged to a median of 36 months, compared to the historical expectation of approximately 24 months.

1.2 To assess the tolerance and efficacy of Y2B8 (Zevalin) after R-FND (rituximab, fludarabine, mitoxantrone, dexamethasone) in patients with high-risk stage III-IV follicular lymphoma

1.3 To assess overall response, failure-free survival, and survival of this strategy compared to our historical experience with FND (fludarabine, mitoxantrone, dexamethasone) alone or R-FND

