## 2.3 Fludarabine and FND Combination

Fludarabine is an active agent for patients with indolent lymphomas; it has been used in the setting of relapse and up-front, and has been used alone and in combination (13,14). The FND combination has been particularly effective and well tolerated (11-13), and is capable of inducing molecular remission (18).

Our sequential experience with FND started with a phase I trial (15) that has defined a dose that has been adopted widely (16, 19-22). We subsequently conducted a phase II trial in the setting of relapse (17), then front-line trials including one in conjunction with rituximab (6, 23, 24). These latter trials (6, 23, 24) provide the framework for the questions to be addressed in the current trial. The FND front-line experience that has the longest follow-up is DM92-103 (23). Based on that trial, we expect a CR rate of about 80%, and a 5-year failure-free survival of about 40%. The R-FND experience (protocol DM97-261) has shorter follow-up; the DM97-261 experience provides the expectation of a molecular response rate of 80% (17,18).

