# **10.0 Statistical Consideration**

10.1.Primary objective and sample size

The objective of this trial is to determine if R-FND followed by Zevalin and rituximab maintenance therapy, is sufficiently efficacious in the treatment of high-risk follicular lymphoma to merit further study in this disease. Although tumor response can be achieved with standard therapy in the majority of patients, these responses are short-lived. Among 729 high-risk patients treated with standard therapy in a multicenter study (including MDACC), the median time to progression (TTP) was 24 months (8). The new regimen would be regarded as a success if median TTP can be prolonged to 36 months or greater. A maximum of 50 patients will be entered on this single arm trial, at an expected accrual rate of 2 patients per month. The trial will require approximately 25 months for patient accrual and an additional 8 months for patient follow-up. If the trial continues to maximum accrual and sufficient follow-up to observe 30 progression events, then a 95% credible interval for median TTP (assumed to be 36 months) would extend from 27.9 to 52.9 months.

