10.3. Analysis

The distribution of TTP will be estimated by the method of Kaplan and Meier, and accompanied by 95% confidence interval. Summary statistics will be computed for response and toxicity endpoints. All patients who receive any chemotherapy will be included in calculation of these endpoints. Patients lost to follow-up are regarded as failures if response has not been measured, and as censored observations at date of loss for purpose of estimating TTP.

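### Does leaving failure-free survival out of the statistical section undermine the trial, given that its quoted benchmark is 40% at 5 years?

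*Combined protocol and SAP*

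**What the plan says.** Objective 1.3 of the protocol reads, in part: "To assess overall response, failure-free survival, and survival of this strategy compared to our historical experience with FND" alone or R-FND. Section 2.3 supplies the history. For the front-line FND trial with the longest follow-up it says "Based on that trial, we expect a CR rate of about 80%, and a 5-year failure-free survival of about 40" per cent. For R-FND it says only "The R-FND experience (protocol DM97-261) has shorter follow-up" and gives a molecular response rate, with no failure-free survival figure.

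Section 10 does not carry the endpoint forward. Section 10.2 states "Additional endpoints are achievement of response (CR + CRu + PR), as defined in Section 8, overall survival, and safety". Section 10.3 states "The distribution of TTP will be estimated by the method of Kaplan and Meier", with a 95% confidence interval, and adds "All patients who receive any chemotherapy will be included in calculation of these endpoints". Failure-free survival is not mentioned. The word failure appears in Section 8.2 as a response category, and in Section 10.3 as the way to score an unmeasured response. Neither is a time-to-event definition.

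On timing, Section 10.1 says "The trial will require approximately 25 months for patient accrual and an additional 8 months for patient follow-up", and also gives a credible interval that assumes follow-up long enough for 30 progressions. Section 7.4 recommends yearly restaging in the long term and says that data will still be sought beyond year 5. The success criterion concerns TTP alone: "The new regimen would be regarded as a success if median TTP can be prolonged to 36 months or greater".

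**The concern.** A stated objective with no definition, method or date leaves the event list, the time point and the comparator to be chosen after the data are seen. Here the worry goes further than a missing line in an endpoint list, because adding a Kaplan-Meier curve would not by itself deliver the comparison:

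- **Timing.** Nobody can have 60 months of follow-up by month 33, and Section 10 sets no later analysis.
- **Level.** A regimen exactly on the 36-month target would have an expected 5-year value below 40%, so it could look worse than FND alone while meeting its own success criterion.
- **Population.** Section 2.3 does not say whether the 40% came from high-risk patients. If it did not, it is a poor comparator. If it did, it is hard to square with the 24-month high-risk median in Section 10.1.

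At stake is the reading of objective 1.3. Failure-free survival is also, apart from overall survival, the only named time-to-event endpoint that could count patients who fail or die without observed progression.

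**Working it through.** **Inputs.** Maximum 50 patients, 2 per month, 8 further months of follow-up, historical median 24 months, target median 36 months, 30 events and the interval 27.9 to 52.9 months (Section 10.1); exponential TTP (Section 10.5); scenario median 48 months (Section 10.4); about 40% at 5 years (Section 2.3).

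**1. Timeline.** Accrual is 50/2 = 25 months, and 25 + 8 = 33 months, which reproduces the plan. At month 33 follow-up runs from 8 to 33 months, so no patient has 60. The last patient reaches 60 months at 25 + 60 = month 85.

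**2. Implied 5-year values.** For median M the exponential model gives S(60) = 2^(−60/M).

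| Median TTP (months) | S(60) |
|---|---|
| 24 | 17.7% |
| 27.9 | 22.5% |
| 36 | 31.5% |
| 48 | 42.0% |
| 52.9 | 45.6% |

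Solving 2^(−60/M) = 0.40 gives M = 60 × ln 2 / (−ln 0.40) = 45.4 months. These are progression-only values. If failure-free survival counts progression and other failures too, it would be equal or lower.

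**3. Dependence on the model.** For a Weibull distribution with median 36, S(60) = 2^(−(60/36)^k). Shape k = 0.75 gives 36.2% and k = 1.25 gives 26.9%; reaching 40% needs k of about 0.55. The shortfall at a median of 36 is therefore not produced by the exponential form alone.

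**4. When data would exist.** With uniform accrual over 25 months and r = ln 2/M, expected events at month T are 50 × [1 − e^(−rT)(e^(25r) − 1)/(25r)]. At M = 36 this gives 16.0 events at month 33. Thirty events are expected at about month 45, 61 or 76 for medians of 24, 36 or 48. The number of patients with at least 60 months of potential follow-up is 2 × (T − 60), limited to between 0 and 50: about 0, 1 and 33 at those dates, and all 50 at month 85.

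**5. How often would an on-target regimen look worse than 40%?** Simulation of 40,000 trials with 50 patients each, no early stopping, an exponential fit and extrapolation to 60 months. Entries are the share of trials with an estimated S(60) below 40%.

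| True median | Month 33 | Month 61 | Month 85 |
|---|---|---|---|
| 36, all trials | 80% | 89% | 92% |
| 36, only trials with estimated median ≥ 36 | 61% | 78–79% | 83–84% |
| 48, all trials | 41% | 39% | 38% |

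At a true median of 48, among trials with an estimated median of at least 36, the share is 32–35%.

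**6. Precision at month 85.** With no losses, the 95% interval around 40% is 0.40 ± 1.96 × √(0.40 × 0.60/50) = 26% to 54%.

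**7. What the plan does with 40%.** It appears once, as background in Section 2.3. No section makes it a threshold, tests against it or extrapolates to it. The exponential model serves the Bayesian updating in Section 10.5; final estimation in Section 10.3 is Kaplan-Meier.

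**The case for a change.** The strongest case for a change is that a single-arm trial which names a historical comparison as an objective should fix the event definition, time point and comparator beforehand, and that the one number quoted invites a misleading reading. The facts behind it stand: the endpoint is missing from Section 10, the arithmetic is right, and at a true median of exactly 36 most trials would show an estimate below 40%. A simple 5-year proportion with complete follow-up gives a similar answer (about 87% of trials), so this does not depend on the exponential fit.

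The inferred harm does not stand. The criterion is 36 months or more, so the high percentages describe its floor; at 48 months the tendency reverses. The objective refers to the institution's own experience with two regimens, so the comparator need not be one rounded figure. The unstated risk mix also weakens the level argument: if the FND patients were not all high-risk, 40% against 31.5% is a difference of population and not an inconsistency. Five-year data are envisaged, since Section 7.4 continues restaging and Section 10.1 contemplates 30 events.

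One could also ask whether patients taken off study without progression (Sections 5.1.6, 5.4.3.5 and 9.1) are still followed for it, and how other therapy or death without progression enters TTP. Those are questions about TTP, no size can be derived for them, and Appendix E, which Section 7.4 cites for the restaging schedule, is not in the text available.

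**Conclusion.** This is a gap that analysts fill sensibly, and no change to the plan is needed. Failure-free survival is one descriptive secondary endpoint. The natural course is to use the definition from the earlier FND and R-FND trials, since comparability with them is the purpose of objective 1.3. A Kaplan-Meier estimate with a 95% interval would then be reported at times that the follow-up supports, and any comparison limited to patients of similar risk. Writing this down would record ordinary practice. A 5-year comparison would remain descriptive in any case: even at month 85 its interval is about ±14 points.

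The apparent conflict amounts to 31.5% against 40%, or 8.5 points, at a true median of exactly 36 months. It disappears at 45.4 months. It rests on exponential TTP, on reading a progression-only value as failure-free survival, and on treating 40% as a matched comparator, which Section 2.3 does not establish. A reader of the final report should not set the result against 40% without knowing the risk mix behind that figure. The TTP success criterion, its Kaplan-Meier analysis and the stopping rule in Section 10.5 make no use of failure-free survival and are unchanged by this point.

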10.3. Analysis

The distribution of TTP will be estimated by the method of Kaplan and Meier, and accompanied by 95% confidence interval. Summary statistics will be computed for response and toxicity endpoints. All patients who receive any chemotherapy will be included in calculation of these endpoints. Patients lost to follow-up are regarded as failures if response has not been measured, and as censored observations at date of loss for purpose of estimating TTP.

#### 10.4. Interim monitoring

The trial will be monitored as often as feasible and will be stopped early if, based on current data, it is unlikely that the median TTP following R-FND followed by Zevalin and rituximab maintenance is at least 12 months longer than that achieved with standard therapy (see section 10.5). The probability criterion is recomputed prior to each patient entry (or as often as possible) and requires updating of TTP information for each patient previously entered. This will be accomplished through a web-based computer program and data entry screen provided by the Department of Biostatistics. In the event of insufficient evidence of the superiority of R-FND followed by Zevalin and rituximab maintenance with regard to TTP, the program will print a statement that no further patients should be accrued to the trial.

To obtain operating characteristics of these monitoring procedures, the trial was simulated using several assumed medians for time to progression, with computer generated patients arriving according to a Poisson process at the rate of 2 patients per month. Results follow:

Median TP (months)	Pr (stop early)	# of Patients	Average trial length (months)
12	0.999	23	11.3
24	0.433	43	21.4
36	0.054	49	24.4
48	0.015	50	24.9

In addition to the ongoing monitoring, a planned interim analysis will be performed on the first 25 patients, to be conducted 13 months after registration of patient 25.

Preliminary reviews of safety will also be done: (a) after the enrollment of 10 patients; and (b) after the first 10 patients complete Zevalin therapy.

10.5 At any point in the trial, TTP can be calculated for each patient, with the time interval regarded as censored at the date of last followup if progression has not been observed for a patient. At each interim analysis, we will apply a Bayesian method of updating prior information with TTP data observed to that time. It is assumed that the TTP for each patient is exponentially distributed with median,  $\lambda_{NEW}$ , for the R-FND followed by Zevalin and rituximab maintenance group and  $\lambda_{H}$  for standard treatment. Based on historical data,  $\lambda_{H}$  is assumed to follow an inverse gamma distribution with mean 24 and variance 16.7. To reflect the little prior knowledge of  $\lambda_{NEW}$ , we assume an inverse gamma distribution with the same mean and variance 100. Since the goal of the study is to increase the median TTP by 12 months, the trial will be stopped early if, based on current data, Pr ( $\lambda_{NEW} > \lambda_{H} + 12$  month data) < 0.03. The probability cutoff of 0.03 was chosen to obtain a 0.054 false negative (early stopping) probability if the true median TTP is 36 months.

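### With the printed priors and 0.03 cutoff, a regimen that meets the 36-month target is stopped early about 18% of the time, not the stated 5.4%

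*Combined protocol and SAP*

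**What the plan says.** Section 10.5 sets out a Bayesian futility rule.

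- **Model:** "It is assumed that the TTP for each patient is exponentially distributed with median" as the parameter. A patient without progression enters "with the time interval regarded as censored at the date of last followup if progression has not been observed for a patient".
- **Prior, standard treatment:** the historical median "is assumed to follow an inverse gamma distribution with mean 24 and variance 16.7".
- **Prior, new regimen:** "we assume an inverse gamma distribution with the same mean and variance 100".
- **Criterion:** because "the goal of the study is to increase the median TTP by 12 months", accrual stops when the posterior probability that the new median exceeds the historical one by more than 12 months falls below 0.03.
- **Justification of the cutoff:** "The probability cutoff of 0.03 was chosen to obtain a 0.054 false negative (early stopping) probability if the true median TTP is 36 months".

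Section 10.4 gives the timing: "The probability criterion is recomputed prior to each patient entry (or as often as possible". It says the trial was simulated "with computer generated patients arriving according to a Poisson process at the rate of 2 patients per month", and it tabulates, for true medians of 12, 24, 36 and 48 months, early-stopping probabilities of 0.999, 0.433, 0.054 and 0.015 with 23, 43, 49 and 50 patients. Section 10.1 caps enrolment at 50. No minimum number of patients or events before the first check is stated.

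**The concern.** The 0.054 rate is the only reason given for choosing 0.03. If the printed rule does not produce it, the cutoff has no stated basis, and the error rates in the protocol do not belong to the design it describes.

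The rule is also operational. Under section 10.4 a web program applies it and tells the investigators to stop accrual. If that program implements section 10.5 as printed, a regimen that truly reaches the 36-month goal is much more likely to be abandoned than stated. If it implements something else, the protocol misdescribes its own stopping rule.

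**Working it through.** **Inputs.** All come from the protocol: priors, model, margin and cutoff from section 10.5; check schedule and accrual from section 10.4; maximum of 50 patients from section 10.1.

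**Step 1: priors by matching moments.** For an inverse gamma with shape a and scale b, the mean is b/(a − 1) and the variance is mean²/(a − 2). Hence a = mean²/variance + 2 and b = mean × (a − 1).

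- Historical median: a = 576/16.7 + 2 = 36.49; b = 24 × 35.49 = 851.8.
- New-regimen median: a = 576/100 + 2 = 7.76; b = 24 × 6.76 = 162.24.

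**Step 2: posterior.** An exponential time with median λ has hazard ln 2/λ. After d progressions in T patient-months, the new-regimen median is inverse gamma with shape 7.76 + d and scale 162.24 + ln 2 × T. The historical prior is not updated. The criterion probability is found by integrating over that prior.

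**Step 3: where the boundary lies.** Before any data the criterion probability is only 0.114. Three progressions in 22 patient-months give shape 10.76 and scale 162.24 + 0.693 × 22 = 177.49, and the probability falls to 0.020, which closes accrual. The rule stops when total follow-up is below these values:

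| Progressions | Stops if patient-months below | Implied observed median, ln 2 × T/d (months) |
|---|---|---|
| 3 | about 41 | 9.5 |
| 5 | 112.1 | 15.5 |
| 10 | 297.8 | 20.6 |
| 20 | 686.5 | 23.8 |

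**Step 4: simulation of the printed rule.** Poisson accrual at 2 per month, at most 50 patients, a check before each entry, stop below 0.03, at least 20,000 trials per row:

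| True median (months) | Stop: printed | Stop: reproduced | Patients: printed | Patients: reproduced | Length: printed (months) | Length: reproduced (months) |
|---|---|---|---|---|---|---|
| 12 | 0.999 | 0.998 | 23 | 18 | 11.3 | 9.3 |
| 24 | 0.433 | 0.60 | 43 | 36 | 21.4 | 18.3 |
| 36 | 0.054 | 0.18 | 49 | 45 | 24.4 | 22.8 |
| 48 | 0.015 | 0.06 | 50 | 48 | 24.9 | 24.1 |

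At 36 months, 100,000 trials gave 0.178 with a Monte Carlo standard error of 0.001, and other seeds gave 0.175 to 0.179. The gap from 0.054 is not simulation noise.

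**Step 5: other readings, stopping probability at 36 months.**

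| Variant (printed priors and cutoff unless noted) | Stop at 36 months |
|---|---|
| First check at 10 / 15 / 20 / 25 patients | 0.174 / 0.166 / 0.155 / 0.137 |
| Checks every 1 / 3 / 6 months | 0.169 / 0.130 / 0.100 |
| Checks every 5 / 10 patients | 0.129 / 0.095 |
| Progression data updated every 2 / 3 / 4 months | 0.145 / 0.134 / 0.123 |
| Evenly spaced arrivals | 0.183 |
| Checks continued 8 months after accrual | 0.19 to 0.20 |
| Parameter treated as the mean throughout | 0.188 |
| Historical median fixed at 24 | 0.245 |

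Two variants come near 0.054, but both contradict the text and miss other rows. A single check at 25 patients gives 0.044, with 0.77 at 12 months and 0.19 at 24. Dropping ln 2 from the posterior while simulating medians gives 0.043, with 0.96 and 0.22.

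**Step 6: cutoff that would deliver 0.054.** With checks during accrual only, a cutoff of about 0.0115 gives 0.992, 0.356, 0.054 and 0.011. With 8 months of further checks after accrual, about 0.010 is needed.

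**The case against.** The strongest reply is that the check schedule is not fixed. Section 10.4 allows recomputation less often than every entry, and the plan says nothing on a minimum sample, data lag or checks after accrual. The 0.18 figure takes the most intensive schedule the text permits.

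This has some force. Checks every 3 to 6 months or every 5 to 10 patients bring the 36-month figure to about 0.09 to 0.13, roughly 1.7 to 2.4 times the stated rate rather than 3.3 times. The 24-month row is also sensitive: checks every 10 patients give about 0.40 to 0.46, which spans the printed 0.433. But the same schedule gives 0.095 at 36 months and 0.98 at 12 months, so it does not recover the table. No schedule tried matches the 12-, 24- and 36-month rows together.

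A second reply is that an input may be misprinted while the table is right. Changing one prior or the cutoff, together with checks after accrual, comes close. A historical variance of 100 gives 0.999, 0.374, 0.053 and 0.012; a cutoff near 0.010 gives 1.000, 0.442, 0.054 and 0.008. Both are conjecture. They show that the written rule and the table disagree without showing which one is wrong, and that the program in use may differ from the text.

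Finally, this is a futility rule. The error raises the risk of discarding an adequate regimen. It does not create a false claim of efficacy, and the Kaplan-Meier estimate in section 10.3 does not depend on the cutoff.

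**Conclusion.** The point holds: the printed rule does not have the printed operating characteristics. With a check before each entry, a regimen with a true median of 36 months is stopped early with probability about 0.18 against 0.054 stated, or roughly one trial in six rather than one in nineteen. On the same reading the figures are about 0.60 against 0.433 at 24 months and 0.06 against 0.015 at 48 months, and at 12 months the trial stops after about 18 patients rather than 23.

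The exact size rests on the check schedule. Under sparser schedules the 36-month figure is still about 0.09 to 0.13. The 24-month discrepancy is the most schedule-dependent; the excess at 36 months persists under every realistic schedule tried. What the web program actually does cannot be determined from the documents.

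**What to change.** Re-run the simulation from the inputs in section 10.5 and compare them with those in the monitoring program. Then make sections 10.4 and 10.5 agree in one of these ways.

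1. **If the original simulation used other inputs** (priors, cutoff, check schedule, a minimum sample, checks after accrual), print those inputs so that the rule matches the table.
2. **If the printed rule is intended, keep 0.03** and replace the table with the reproduced values: stopping 0.998, 0.60, 0.18 and 0.06; mean patients 18, 36, 45 and 48; lengths as reproduced above. Correct the sentence that claims 0.054.
3. **If a 0.054 false-negative rate is intended, reset the cutoff** to about 0.0115 (about 0.010 if checks continue for 8 months after accrual). At 0.0115, state that stopping at a true median of 24 months is about 0.36, a real loss of protection against continuing with an inactive regimen.

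In every case, state the check schedule that was simulated. The cost is one simulation and edits to the table and text of sections 10.4 and 10.5. No patients are added, but the stated error rates become less favourable under options 2 and 3.
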